7.2.3. Liver-related Laboratory Evaluations

Liver-related abnormalities after initial study drug dosing will be examined and summarized using the number and percentage of subjects who were reported to have the following laboratory test values for post-baseline measurements:

- Aspartate aminotransferase (AST): (a) > 3 times of the upper limit of reference range (ULN); (b) $> 5 \times$ ULN; (c) $> 10 \times$ ULN; (d) $> 20 \times$ ULN
- Alanine aminotransferase (ALT): (a) $> 3 \times$ ULN; (b) $> 5 \times$ ULN; (c) $> 10 \times$ ULN; (d) $> 20 \times$ ULN

- AST or ALT: (a) $> 3 \times \text{ULN}$; (b) $> 5 \times \text{ULN}$; (c) $> 10 \times \text{ULN}$; (d) $> 20 \times \text{ULN}$
- Total bilirubin: (a) $> 1 \times \text{ULN}$; (b) $> 2 \times \text{ULN}$
- Alkaline phosphatase (ALP) $> 1.5 \times \text{ULN}$
- AST or ALT $> 3 \times \text{ULN}$ and total bilirubin: (a) $> 1.5 \times \text{ULN}$; (b) $> 2 \times \text{ULN}$
- AST or ALT $> 3 \times \text{ULN}$, total bilirubin $> 2 \times \text{ULN}$ and ALP $< 2 \times \text{ULN}$

The summary will include data from all post-baseline visits up to and including Day 28. For individual laboratory tests, subjects will be counted once based on the most severe post-baseline values. For both the composite endpoint of AST or ALT and total bilirubin, subjects will be counted once when the criteria are met at the same post-baseline visit date. The denominator is the number of subjects in the Safety Analysis Set who have nonmissing post-baseline values of all relevant tests at the same post-baseline visit date. A listing of subjects who met at least 1 of the above criteria will be provided.

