7.2.2.1. Treatment-Emergent Laboratory Abnormalities

Treatment-emergent laboratory abnormalities are defined as values that increase at least 1 toxicity grade from baseline at any postbaseline time point, up to and including Day 28. If the relevant baseline laboratory value is missing, any abnormality of at least Grade 1 observed within the time frame specified above will be considered treatment emergent.

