15.11.6.2.2	Chemistry Test: AST (U/L) and Change from Baseline	Safety Analysis Set
15.11.6.2.3	Chemistry Test: ALP (SGPT) (U/L) and Change from Baseline	Safety Analysis Set
15.11.6.2.4	Chemistry Test: Total Bilirubin (mg/dL) and Change from Baseline	Safety Analysis Set
15.11.6.2.5	Chemistry Test: Blood Urea Nitrogen (mg/dL) and Change from Baseline	Safety Analysis Set
15.11.6.2.6	Chemistry Test: Creatinine (mg/dL) and Change from Baseline	Safety Analysis Set
15.11.6.2.7	Chemistry Test: Creatinine Clearance (mL/min) and Change from Baseline	Safety Analysis Set
15.11.6.2.8	Chemistry Test: Albumin (g/dL) and Change from Baseline	Safety Analysis Set
15.11.6.2.9	Chemistry: Creatinine (mg/dL) and Change from Baseline by Hourly Timepoint for Hospitalized Subjects	Safety Analysis Set
15.11.6.4.1.1	Treatment Emergent Laboratory Abnormalities	Safety Analysis Set
15.11.6.4.1.2	Treatment Emergent Laboratory Abnormalities by Age Group (<65 Years or ≥ 65 Years)	Safety Analysis Set
15.11.6.4.1.3	Treatment Emergent Laboratory Abnormalities by Sex (Male or Female)	Safety Analysis Set
15.11.6.4.2	Treatment Emergent Grade 3 or Above Laboratory Abnormalities	Safety Analysis Set
15.11.6.4.3	Treatment Emergent Marked Laboratory Abnormalities	Safety Analysis Set
15.11.6.5	Liver-Related Laboratory Abnormalities	Safety Analysis Set

Table Number	Title	Analysis Set
15.11.6.6	Shift in Troponin Results	Safety Analysis Set
15.11.7.1.1	Vital Signs: Diastolic Blood Pressure (mmHg) and Change from Baseline	Safety Analysis Set
15.11.7.1.2	Vital Signs: Systolic Blood Pressure (mmHg) and Change from Baseline	Safety Analysis Set
15.11.7.1.3	Vital Signs: Pulse (beats per minute) and Change from Baseline	Safety Analysis Set
15.11.7.1.4	Vital Signs: Respiratory Rate (breaths per minute) and Change from Baseline	Safety Analysis Set
15.11.7.1.5	Vital Signs: Temperature (Celsius) and Change from Baseline	Safety Analysis Set
15.11.7.2.1	Body Weight (kg) and Change from Baseline	Safety Analysis Set
15.11.7.3.1	Prior Medications by Drug Class and Preferred Drug Name	Safety Analysis Set
15.11.7.3.2	Concomitant Medications by Drug Class and Preferred Drug Name	Safety Analysis Set
15.11.7.3.3	Prior Ribavirin	Safety Analysis Set
15.11.7.3.4	Concomitant Ribavirin	Safety Analysis Set
15.11.9.1	Shift in Electrocardiogram Results	Safety Analysis Set
15.11.9.2	Subject with New Abnormalities ECG at Postbaseline	Safety Analysis Set

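### The liver table does not separate new from pre-existing abnormalities, and its combined AST/ALT-plus-bilirubin rows have no baseline-relative counterpart in the SAP (minor)

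*SAP*

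**What the plan says.** Section 7.2.3 introduces the liver summary as follows: "Liver-related abnormalities after initial study drug dosing will be examined and summarized using the number and percentage of subjects". It then lists multiples of the upper limit of normal (ULN) for AST, ALT, total bilirubin and ALP. The combined rows are AST or ALT above 3 x ULN with bilirubin above 1.5 x or 2 x ULN, and AST or ALT above 3 x ULN with bilirubin above 2 x ULN and ALP below 2 x ULN.

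The counting rules are:

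- Single tests: "For individual laboratory tests, subjects will be counted once based on the most severe post-baseline values".
- Combined AST/ALT and bilirubin: "subjects will be counted once when the criteria are met at the same post-baseline visit date".
- Denominator: "The denominator is the number of subjects in the Safety Analysis Set who have nonmissing post-baseline values of all relevant tests", on the same post-baseline date.
- Listing: "A listing of subjects who met at least 1 of the above criteria will be provided".

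Section 12.1 lists the output as Table 15.11.6.5, titled "Liver-Related Laboratory Abnormalities". Section 7.2.2.1, by contrast, defines the treatment-emergent graded abnormalities relative to baseline: "values that increase at least 1 toxicity grade from baseline at any postbaseline time point".

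**The concern.** The opening sentence of 7.2.3 fixes when the value is measured, not that the abnormality is new. A subject above a threshold on Day 1 who is unchanged or even improving at a later visit, but still above it, enters the table exactly as a new case does.

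Most other safety summaries in the SAP use baseline. Graded abnormalities need a rise of at least 1 grade (7.2.2.1), and marked abnormalities a rise of at least 3 (7.2.2.2). Numeric results are shown with change from baseline (7.2.1). ECG and troponin results get shift tables (7.5, 7.6). The liver table has neither a baseline condition nor a shift.

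This matters most for the combined rows. Whether AST/ALT and bilirubin were raised on the same date cannot be recovered from separate tables for each analyte, and Table 15.11.6.5 is the only planned by-arm summary of that criterion. Carried-over subjects add a background to both arms that pulls the risk ratio toward 1. In arms of about 30, a chance difference in that background also shows up as a difference between arms. Section 7.2 plans no formal testing of laboratory data, so the displayed counts are what a reader will judge by.

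**Working it through.** **Text check.** The SAP states no figure for this table, so there is none to reproduce. The sections compare as follows.

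| Summary | Baseline used? | Covers the combined criteria? |
|---|---|---|
| 7.2.1, Tables 15.11.6.2.1 to 15.11.6.2.4 (ALT, AST, ALP, bilirubin) | Yes, change from baseline | No, one analyte each |
| 7.2.2.1, Table 15.11.6.4.1.1 | Yes, rise of at least 1 grade | No |
| 7.2.2.2, Table 15.11.6.4.3 | Yes, rise of at least 3 grades | No |
| 7.2.3, Table 15.11.6.5 | No | Yes |

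No planned table is both baseline-relative and joint across analytes.

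**Inputs for the illustration**

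- n = 30 per arm: 60 subjects randomized 1:1 (Sections 1.2 and 1.3).
- p = share of subjects who meet a criterion at baseline and still meet it at some post-baseline visit. This is not in the SAP; 0.5% to 10% is assumed.
- New-onset risk among the remaining subjects: 5% v 15%, a ratio of 3.0. This is assumed and used only to show dilution.

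**Chance imbalance.** Let X and Y be the carried-over subjects in the two arms, independent Binomial(30, p). The expected number per arm is 30p, and P(|X - Y| >= 2) is obtained by enumeration.

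**Dilution.** The tabulated risk is p + (1 - p)q, with q = 0.05 or 0.15. At p = 5% this gives 0.05 + 0.95 x 0.05 = 0.0975 and 0.05 + 0.95 x 0.15 = 0.1925, a ratio of 0.1925/0.0975 = 1.97. At p = 10% it gives 0.145 and 0.235, a ratio of 1.62.

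**Expected excess.** The expected excess of subjects in the arm with the higher risk is 30 x (1 - p) x 0.10.

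| p | Carried over per arm, 30p | P(arms differ by 2 or more) | Tabulated ratio (new-onset ratio 3.0) | Expected excess subjects |
|---|---|---|---|---|
| 0.5% | 0.15 | 1.7% | 2.82 | 2.99 |
| 1% | 0.3 | 5.5% | 2.66 | 2.97 |
| 3% | 0.9 | 23% | 2.24 | 2.91 |
| 5% | 1.5 | 35% | 1.97 | 2.85 |
| 10% | 3.0 | 51% | 1.62 | 2.70 |

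The ratio falls steadily with p. The expected excess count barely moves, and it is the same whether all subjects or only those below the criterion at baseline are tabulated. Carried-over subjects therefore add noise around that excess and shrink the ratio, but they do not remove the excess.

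**The case against.** The strongest defence is that nothing here is misstated. Section 7.2.3 says that it counts post-baseline values, and the table title does not claim that they are treatment-emergent, unlike the titles of the 15.11.6.4 series. Counting every value above a threshold is a defensible screen, because it misses no severe value. That stands, and it is why the current rows should stay.

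Several further points also stand:

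- For single tests, the graded treatment-emergent tables and the change-from-baseline tables largely do what the liver table does not.
- Individual results are in the chemistry listings by subject and visit (Section 7.2), so with 60 subjects anyone in a combined row can be traced to Day 1 by hand. That is a route for checking, not a by-arm summary.
- The combined criteria may be rare at baseline. At 0.5% or 1%, a difference of 2 or more carried-over subjects is unlikely. Any eligibility limit on liver tests would be in the protocol, which is not shown.
- No test or decision rule is affected.

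A reader might infer that the table biases the comparison, or that it would by itself hide or create a hepatic signal. The documents do not support that. Allocation is 1:1 against placebo, so the expected background is the same in both arms. A subject abnormal before dosing is counted only if a later value also meets the criterion. Other planned outputs allow single-analyte findings to be checked.

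**Conclusion.** The point holds as a minor reporting weakness. Table 15.11.6.5 mixes new and pre-existing abnormalities, and for the same-date AST/ALT-plus-bilirubin rows, including the row with ALP, no other planned table separates them. The consequence is dilution of the risk ratio and extra chance imbalance, not systematic bias.

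The size cannot be fixed from the SAP. On the assumed range it runs from negligible (about a 2% chance of a difference of 2 or more carried-over subjects at 0.5% prevalence) to substantial (51% at 10%). These figures assume 30 subjects per arm, persistence of the abnormality to at least one post-baseline visit, and independence between arms. The upper part of the range has no support in the SAP for the combined rows. The case for changing the table rests on how little the change costs.

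**What to change.** In Section 7.2.3 and Table 15.11.6.5:

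1. Keep all current rows.
2. For the combined criteria at least, and preferably for every ULN-multiple row, add the number and percentage of subjects who meet the criterion after baseline but did not meet it at baseline.
3. Use as the denominator the subjects not meeting the criterion at baseline who have the relevant post-baseline values under the existing rule. Treat a missing baseline as not meeting the criterion, in line with how 7.2.2.1 treats a missing baseline grade.
4. Show baseline values of the relevant tests in Listing 16.2.8.1.6.

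The cost is a sentence or two in the SAP, some extra rows and a listing column. Central safety chemistry is already drawn on Day 1 (Appendix 1), so no new data are needed. The only downside is that the added rows have slightly smaller denominators.

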7.3. Body Weight and Vital Signs

Descriptive statistics will be provided by treatment group for body weight and vital signs as follows:

- Baseline value
- Values at each postbaseline time point
- Change from baseline at each postbaseline time point

Median (Q1, Q3) of the observed values for vital signs will be plotted by treatment group and visit.

A baseline value will be defined as the last available value collected on or prior to the date/time of first dose of study drug. Change from baseline to a post-baseline visit will be defined as the post-baseline value minus the baseline value.

In the case of multiple values at a visit assessment, data will be selected for analysis as described in Section 3.8.3. No inferential statistics will be generated.

A by-subject listing of vital signs will be provided by subject ID number and visit in chronological order. Body weight will be included in the vital signs listing, if space permits. If not, they will be provided separately.

7.4. Prior and Concomitant Medications

Medications collected at screening and during the study will be coded using the current version of the World Health Organization (WHO) Drug dictionary.

7.4.1. Prior Medications

Prior medications are defined as any medications taken before a subject took the first study drug.

Prior medications will be summarized by Anatomical Therapeutic Chemical (ATC) drug class Level 2 and preferred name using the number and percentage of subjects for each treatment group and overall. A subject reporting the same medication more than once will be counted only once when calculating the number and percentage of subjects who received that medication. The summary will be ordered alphabetically by ATC classes and then by preferred term in order of descending overall frequency within each ATC medical class. For drugs with the same frequency, sorting will be done alphabetically.

For the purposes of analysis, any medication with a start date prior to the first dosing date of study drug will be included in the prior medication summary regardless of when the stop date is. If a partial start date is entered the medication will be considered prior unless the month and year (if day is missing) or year (if day and month are missing) of the start date are after the first dosing date. Medications with a completely missing start date will be included in the prior medication summary, unless otherwise specified. Summaries will be based on the Safety Analysis Set. No formal statistical testing is planned.

Prior ribavirin use will be summarized separately from other prior general medications.

7.4.2. Concomitant Medications

Concomitant medications are defined as medications taken while a subject took study drug. Use of concomitant medications will be summarized by Anatomical Therapeutic Chemical (ATC) drug class Level 2 and preferred name using the number and percentage of subjects for each treatment group. A subject reporting the same medication more than once will be counted only once when calculating the number and percentage of subjects who received that medication. The summary will be ordered alphabetically by ATC medical class and then by preferred term in descending overall frequency within each ATC medical class. For drugs with the same frequency, sorting will be done alphabetically.

For the purposes of analysis, any medication with a start date prior to or on the first dosing date of study drug and continued to take after the first dosing date, or started after the first dosing date but prior to or on the last dosing date of study drug will be considered concomitant medications. Medications started and stopped on the same day as the first dosing date or the last dosing date of study drug will also be considered concomitant. Medications with a stop date prior to the date of first dosing date of study drug or a start date after the last dosing date of study drug will be excluded from the concomitant medication summary. If a partial stop date is entered, any medication with the month and year (if day is missing) or year (if day and month are missing) prior to the date of first study drug administration will be excluded from the concomitant medication summary. If a partial start date is entered, any medication with the month and year (if day is missing) or year (if day and month are missing) after the study drug stop date will be excluded from the concomitant medication summary. Medications with completely missing start

and stop dates will be included in the concomitant medication summary, unless otherwise specified. Summaries will be based on the Safety Analysis Set. No formal statistical testing is planned.

Concomitant ribavirin use will be summarized separately from other concomitant general medications.

All prior and concomitant medications (other than per-protocol study drugs) will be provided in a by-subject listing sorted by subject ID number and administration date in chronological order.

7.5. Electrocardiogram Assessment

Number and percent of subjects with new ECG abnormalities at postbaseline visits including those assessments obtained for the purpose of standard of care will be summarize by treatments. Only subjects with baseline ECG assessments will be included in this analysis.

A shift table of the central assessment of ECG results at postbaseline visit including those assessments obtained for the purpose of standard of care compared with baseline values will be presented by treatment group using the following categories: normal, no new abnormality, new abnormality, or missing. The number and percentage of subjects in each cross-classification group of the shift table will be presented. Subjects with a missing value at baseline or postbaseline will not be included in the denominator for percentage calculation. No formal statistical testing is planned.

A by-subject listing for ECG central assessment and ECG abnormalities, including those not required by the protocol (ie. standard of care), will be provided by subject ID number and time point in chronological order.

7.6. Other Safety Measures

A shift table of troponin results at postbaseline visit including those obtained for the purposes of standard of care compared with baseline values will be presented by treatment group using the following categories: normal, abnormal, or missing. The number and percentage of subjects in each cross-classification group of the shift table will be presented. Subjects with a missing value at baseline or postbaseline will not be included in the denominator for percentage calculation. No formal statistical testing is planned.

If multiple troponin results exist for one visit due to multiple troponin assay tests performed, the results obtained from Troponin I test will be used for the analysis.

A by-subject listing for all troponin results, including those not required by the protocol (ie, standard of care), will be provided by subject ID number and visit in chronological order.

A data listing will be provided for subjects experiencing pregnancy during the study.

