3.8.2. Analysis Visit

The nominal visit as recorded on the eCRF will be used when data are summarized by visit. Any data relating to unscheduled visits will not be assigned to a particular visit or time point. However, the following exception will be made:

- An unscheduled visit prior to the first dosing of study drug may be included in the calculation of the baseline value, if applicable.
- Unscheduled visits after the first dose of study drug will be included in determining the maximum post-baseline toxicity grade.

- For subjects who prematurely discontinue from the study, early termination (ET) data will be assigned to the next scheduled visit where the respective data were scheduled to be collected.
- Data collected on an extended viral load monitoring visit will be summarized as a separate visit, and labeled as Day 35, 42, 49, or 56.

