3.8.3. Selection of Data in the Event of Multiple Records

Depending on the statistical analysis method, single values may be required for each analysis visit. If multiple valid, nonmissing, continuous measurements exist in one visit, records will be chosen based on the following rules if a single value is needed:

- In general, the baseline value will be the last nonmissing value on or prior to the first dosing date of study drug, unless specified differently. If multiple measurements occur on the same day, the last nonmissing value prior to the time of first dosing of study drug will be considered as the baseline value. If these multiple measurements occur at the same time or the time is not available, the average of these measurements (for continuous data) will be considered the baseline value. For the efficacy endpoints, if no measurements occur prior to the time of first dosing of study drug, the first nonmissing value on the first dosing date of study drug will be considered as the baseline value.
- For postbaseline values:
 - The record closest to the nominal day for that visit will be selected.
 - If there are 2 records that are equidistant from the nominal day, the later record will be selected.
 - If there is more than 1 record on the selected day, the average will be taken, unless otherwise specified.

If multiple valid, non-missing, categorical measurements exist for one visit, records will be chosen based on the following rules if a single value is needed:

- For baseline, the last available record on or prior to the date of the first dose of study drug will be selected. If there are multiple records at the same time or no time recorded on the same day, the value with the lowest severity will be selected unless otherwise specified.
- For postbaseline values:
 - The record closest to the nominal day for that visit will be selected.
 - If there are 2 records that are equidistant from the nominal day, the later record will be selected.
 - If there is more than 1 record on the selected day, the value with the worst severity will be used.

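### The troponin shift table is meant to include standard-of-care results, but the SAP's general visit rules can leave abnormal ones out and Section 7.6 gives no rule to prevent it

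*SAP*

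**What the plan says.** SAP Section 7.6 describes the troponin output as "A shift table of troponin results at postbaseline visit including those obtained for the purposes of standard of care compared with baseline values", tabulated by treatment group "using the following categories: normal, abnormal, or missing". Subjects with a missing baseline or post-baseline value leave the percentage denominator. The one selection rule specific to troponin is a preference for Troponin I when several assays were run for one visit. Section 7.5 uses nearly the same construction for ECG: "A shift table of the central assessment of ECG results at postbaseline visit including those assessments obtained for the purpose of standard of care".

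Two general sections govern how results reach a visit:

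- Section 3.8.2: "The nominal visit as recorded on the eCRF will be used when data are summarized by visit", and "Any data relating to unscheduled visits will not be assigned to a particular visit or time point". It lists exceptions. The one for unscheduled post-dose results reads "Unscheduled visits after the first dose of study drug will be included in determining the maximum post-baseline toxicity grade". The others cover pre-dose baseline values, early-termination data and extended viral monitoring.
- Section 3.8.3: where a visit holds several records, "records will be chosen based on the following rules if a single value is needed". For post-baseline values, "The record closest to the nominal day for that visit will be selected". For categorical data, the worst severity decides only among records on the selected day.

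In the list of tables (Section 12.1), Table 15.11.6.6 is the only one that names troponin. Listing 16.2.8.1.8 covers individual results, and Section 7.6 says that it includes those not required by the protocol.

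**The concern.** Section 7.6 sets an aim without the rule needed to meet it. Standard-of-care results are the ones most likely to fall outside the scheduled visits, and the conventions in Sections 3.8.2 and 3.8.3 were written to exclude off-schedule data or to prefer data near the nominal day. Neither convention looks at whether a result is abnormal.

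At stake is the completeness of the by-arm troponin summary. Appendix 1 marks troponin at baseline and at only two post-baseline visits, so an abnormality that arises and resolves between scheduled tests can be seen only through standard-of-care testing. If such a result is left out, the subject is shown as normal, or as missing and so outside the denominator. Cardiac events are a declared interest (Section 7.1.7 and Appendix 2), and the planned later DMC safety reviews were not held (Section 7.7), so the final by-arm safety tables carry more weight.

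**Working it through.** The SAP gives no figure to reproduce here. The check applies Sections 3.8.2, 3.8.3 and 7.6 to each way in which an abnormal post-dose standard-of-care troponin could be recorded.

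1. **Recorded as unscheduled.** Section 3.8.2 gives it no visit. The toxicity-grade exception does not help, because the table classifies results as normal or abnormal and uses no grade. The result has no cell in the table. If the subject has no other post-dose troponin, the subject is also missing and leaves the denominator.
2. **Recorded under a visit that also has a scheduled result nearer the nominal day.** Example: abnormal on Day 25 and scheduled normal on Day 28, both entered under Day 28. The distances are |25 − 28| = 3 days and |28 − 28| = 0 days. If one value per visit is needed, Section 3.8.3 selects the Day 28 record and the subject counts as normal. The abnormal result is left out.
3. **Recorded on the same day as the selected record.** The worst severity is used, so the abnormal result is kept, unless it comes from another assay and a Troponin I result exists for that visit.
4. **Recorded under a visit with no scheduled troponin.** It is the only record there, so nothing displaces it. It can be tabulated if the table shows that visit or pools across visits.
5. **Collected at early termination.** Section 3.8.2 moves it to the next visit at which the test was scheduled, so it can be kept.

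Cases 1 and 2 leave an abnormal result out, and cases 3 to 5 can keep it. Which case is common depends on how the eCRF records standard-of-care tests, and the SAP does not show this.

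The same steps apply to the ECG shift table in Section 7.5. ECG has a further output, Table 15.11.9.2, which counts subjects with new post-baseline abnormalities. Section 7.5 words that count almost as it words the shift table, so it should not be assumed that the count escapes Section 3.8.2.

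**The case against.** The best reply is that a specific instruction outranks a general one. Section 7.6 expressly includes standard-of-care results, and reading Section 3.8.2 as cancelling that would leave the words with little purpose. Section 3.8.3 applies only if a single value is needed, and the title of Table 15.11.6.6 does not say that it is by visit, so one row per subject is not excluded.

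This reply has force, but it settles only whether the results are included. Section 7.6 gives no placement rule and no worst-value rule. Once a result is included under a visit, Section 3.8.3 can still replace it with a nearer scheduled one. Two programmers could build different tables from the same text.

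A second reply is that other outputs limit the harm. All troponin results are listed by subject, and cardiac adverse events are summarised by arm (Tables 15.11.2.4 and 15.11.4.4). This stands as mitigation. A listing gives no by-arm comparison, however, and the adverse event tables count only what investigators report as events.

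A reader might go further and infer any of the following, which the SAP does not support:

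- That every abnormal result between visits is lost. Cases 3 to 5 above can survive.
- That troponin has a 16-day gap after the first dose. That interval comes from the ECG schedule (Day 1 to Day 17, 17 − 1 = 16); the troponin row in the text at hand may be misaligned.
- That injury is understated more in one arm. Nothing in the SAP shows this.

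**Conclusion.** The concern holds in a limited form. As written, the general rules leave an abnormal standard-of-care troponin out of the only by-arm troponin table in two situations: when it is recorded as unscheduled, and when it shares a visit with a scheduled result nearer the nominal day and one value per visit is taken. The ECG shift table has the same weakness. The results remain in the report through the listing, so the defect is confined to the summary by treatment group.

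The number of subjects affected cannot be derived, because the SAP gives neither the frequency of standard-of-care testing nor the way it is entered. As a scale only: if the 60 enrolled subjects split evenly and all were in the denominator, one subject would be 1/30 = 3.3 percentage points of an arm, and more where missing values shrink the denominator. That even split and full denominator are assumptions.

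The conclusion rests on reading Section 7.6 together with the general rules, since it states no replacement for them. Even if it overrides Section 3.8.2, the choice among several results is not protected. Efficacy analyses are not touched.

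**What to change.** - In Sections 7.5 and 7.6, state that the shift table shows, for each subject, baseline against the worst post-dose result through Day 28 over all scheduled and standard-of-care results.
- In Section 7.6, say how this works with the Troponin I preference, for example by applying that preference only among assays from the same sample or day.
- In Section 3.8.2, add ECG and troponin to the exceptions for unscheduled post-dose results.
- Keep a panel by scheduled visit beside the worst-result table if it is wanted.

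The cost is SAP wording and one extra derivation before the blind is broken. The results are already collected for the listings, so no new data are needed. One small downside is that a worst-value count depends on how often subjects are tested; a table footnote should say so.
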